6.2 Secondary Endpoints

- Time to onset of action defined as first day of active treatment on which MSS shows statistically significant difference from placebo
- MSS development over the course of the study
- SNOT-22 by visit and changes versus baseline
- Percentage of responders and non-responders to treatment based on the assessment of overall response to treatment by the investigator.

6.3 Safety Endpoints

- Incidence and severity of adverse events
- Incidence and severity of drug-related adverse events
- Clinically relevant changes in laboratory parameters, vital signs, physical and ENT examination parameters from Visit 1 to Visit 6 (or early termination)
- Overall assessment of tolerability by patient and by investigator.

7 Statistical Analysis Conventions

7.1 Population for Analysis

7.1.1 Safety Set

The **Safety Set (SS)** is defined as all randomized patients who receive at least one dose of the trial medication. This will be the primary dataset for the evaluation of safety.

7.1.2 Full Analysis Set (FAS)

The **Full Analysis Set (FAS)** is defined as all randomized patients who receive at least one dose of the trial medication and who have at least one post-baseline assessment of MSS during the double-blind treatment period. This will be the primary dataset for comparison of the primary endpoint.

7.1.3 Per Protocol Set

The **Per Protocol Set (PPS)** is defined as all FAS-evaluable patients who complete the double-blind treatment period without major protocol violations (see Section 7.2.7) that could affect the efficacy evaluation, which include the availability of measurements of the primary endpoints. The latter will be prospectively defined before unblinding the trial.

7.2 Statistical Analysis Methods

7.2.1 Listings and Descriptive Statistics

All original and derived parameters as well as population characteristics will be listed.

Data will be described using summary statistics as described in the following sections. For qualitative variables frequency tables (with absolute numbers and percentages) will be created. For quantitative variables descriptive statistics (number of non-missing observations [n], arithmetic mean, standard deviation, median, minimum and maximum) will be calculated.

The standards used to support electronic data submission (e.g., clinic data, diagnostic lab data, efficacy data) will be based on the available version from the Clinical Data Interchange Standards Consortium (CDISC). The versions to be used during the course of this study will stay the same. The current versions are:

- Study Data Tabulation Model (SDTM) v1.6,
- Study Data Tabulation Model Implementation Guide (SDTM IG) v3.2,
- CDISC SDTM Controlled Terminology, 2019-09-27
- Analysis Data Model (ADaM) v2.1,
- Analysis Data Model Implementation Guide (ADaM IG) v1.1,
- The ADaM Basic Data Structure for Time-to-Event Analyses v1.0
- ADaM Structure for Occurrence Data (OCCDS) v1.0
- CDISC ADaM Controlled Terminology, 2019-09-27
- Define-XML v2.0.

A Validation Report (using Pinnacle 21 Community, latest version) and respective Reviewer's Guides (Study Data Reviewers Guide and Analysis Data Reviewers Guide) will be prepared.

7.2.2 Rounding and Decimal Places

All raw data will be listed according to the number of decimal places presented in the source data (i.e. CRF, AE/SAE Report, SNOT diary).

In general, the following rules regarding summary statistics will be applied, unless otherwise stated:

- Mean and median will be tabulated to one more decimal place than the source data,
- Minimum and maximum will be tabulated to the same number of decimal places as the source data,

- Standard deviation will be tabulated to two more decimal places than the source data,
- Coefficient of variation (CV)%, if applicable will be presented to one decimal place.

The primary endpoint mean change will be rounded to 3 decimal places in listings and for further calculations (see section 7.4)

7.2.3 Statistical Significance Level

All statistical tests and comparisons are evaluated at the 5% significance level ($\alpha = 5\%$) if not stated otherwise.

7.2.4 Software

All statistical analysis will be performed using Statistical Analysis Software (SAS) Version 9.4 or higher.

7.2.5 Missing Data

In principle there will be no imputation of missing data.

For evaluation of the primary endpoint in the FAS population the last observation carried forward (LOCF) - principle will be applied.

If any patient terminates the trial before completing the 14 days of double-blind treatment, the last available post-baseline assessment of the MSS will be carried forward until the virtual last observation point, that means the last available post-baseline MSS (i.e. the respective rating of each of the symptoms) will be carried forward for the calculation of the mean change of the MSS.

For missing assessments of single symptoms which are missing between non-missing assessments, the same will be applied. I.e. the last non-missing score will be kept (which implies non-improvement).

With respect to the evaluation of the secondary endpoints in the FAS the following will be applied:

SNOT-22 score - in case of missing item values for the calculation of the score the worst item category will be used if not more than two item values are missing, otherwise the score will be regarded as missing.

Percentage of responders and non-responders: Missing values for the investigator's assessment of the overall response to treatment will be set to the worst case (1-major deterioration, i.e. considered as non-responder)

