- **Major Symptom Score (MSS) assessment by the patient (transcribed by the investigator from TSSF into the CRF, and constituting the baseline value)**
- dispensation of the patient diary
- **SNOT-22 questionnaire on Day 1** (documented by patient in the diary during the visit in the clinical site)
- dispensation of a patient study identification card
- **Randomization to double-blind treatment**
 - **dispensation of the Patient Kit (box) containing the double-blinded trial medication for 14 days and including the separate Replacement/Reserve medication box with 3 Daily Kits**
 - **first intake of 2 tablets solved in 200 mL of water (morning dose of Daily Kit 1) in the presence of the investigator during the intake of breakfast. A pre-packed snack (e.g. croissant or similar) and a small beverage will be provided to the patient for breakfast.**
 - patient instructions for further intake of medication at home with the breakfast and lunch, for daily documentation of MSS in the diary and for correct storage of medication at home
 - patient instructions for return of the diary and the used medication at next visit for investigator's check.

VISIT 3 (Day 4)

The following procedures will be performed and documented in on this day:

- date and time of examination (visit)
- patient identification by means of national ID card or other national ID document
- vital signs measurements of body temperature with documentation of the measuring method used, pulse rate, and blood pressure after 5 minutes rest in sitting position
- documentation of any changes in the concomitant therapy(ies)/ medication(s) or use of other therapeutic measures/ actions
- adverse event questioning

- check of exclusion/ withdrawal criteria and further patient eligibility
- **review of the Patient Diary entries and compliance check; check of the correct documentation of Major Symptom Score (MSS) recorded by the patient once a day before intake of the morning dose**
- **detach the originals of the completed patient diary pages (top pages) and retain in the ITF until the final shipment of the complete diary to [REDACTED] for data entry in the clinical database. The no-carbon copy paper diary pages remain in the ITF of the clinical center.**
- assessment of the overall response to treatment (investigator)
- check of the returned used Daily Kits

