7.4.2.3 SNOT-22 by visit and changes versus baseline

The total scores (sum of all single assessments per subject) will be analyzed descriptively by treatment group and assessment day (Day 1 - Baseline, Day 7 and Day 14).

The change versus baseline will be determined individually as

$$change_{SNOT,day} = \frac{SNOT_{day} - SNOT_{baseline}}{SNOT_{baseline}} * 100\%,$$

where $SNOT_{day}$ denotes the SNOT Score on Day 7 or Day 14.

The percent change will be analyzed descriptively by treatment group and visit for the FAS and the PPS.

The mean SNOT values by treatment and visit will be presented in a graphic containing the curves for all four treatment groups.

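### The worst-category rule for missing SNOT-22 items does not exempt Day 1, so a blank baseline item overstates improvement while a later blank understates it

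*SAP*

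**What the plan says.** SAP 7.2.5 introduces its rules for secondary endpoints with "With respect to the evaluation of the secondary endpoints in the FAS the following will be applied". For the SNOT-22 score it then states that "the worst item category will be used if not more than two item values are missing, otherwise the score will be regarded as missing". No assessment day is named and none is excluded.

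SAP 7.4.2.3 forms the total as the sum of the items, to be "analyzed descriptively by treatment group and assessment day (Day 1 - Baseline, Day 7 and Day 14"). It defines change for each patient as the Day 7 or Day 14 score minus the Day 1 score, divided by the Day 1 score, times 100%. It adds: "The percent change will be analyzed descriptively by treatment group and visit for the FAS and the PPS". The Day 1 score is thus both the reference and the denominator.

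Nothing else in the documents sets a different rule for baseline items. Protocol 10.1 leaves missing-data handling to the SAP, and Protocol 10.3.2 mentions only LOCF for secondary endpoints where relevant.

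**The concern.** Worst-value imputation is normally chosen so that a gap cannot help the result. Its neighbours in SAP 7.2.5 work that way: a missing single MSS symptom keeps its last score, which the SAP notes implies no improvement, and a missing investigator rating counts as non-response. For a change score, that logic holds only after baseline. On Day 1 the worst category makes the patient look sicker at the start, and the later fall looks larger than it was. One rule therefore pushes the change in opposite directions, depending on which form has the gap.

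At stake is the accuracy of the SNOT-22 totals, percent changes and mean curves reported by arm in the FAS and PPS (SAP 8.1 and 8.2). SAP 7.2.5 and 7.4.2.3 plan no SNOT-22 sensitivity analysis that would show the effect.

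**Working it through.** The plan states no numerical expectation for SNOT-22, so there is no figure of its own to reproduce. Its only design figure, 225 per group, concerns the MSS and does not enter here.

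**Inputs from the SAP.** Up to two missing items are set to the worst category (7.2.5). The total is a sum, and change is a percentage of the Day 1 total (7.4.2.3).

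**Assumptions, because the documents are silent.** There are 22 items, as the name implies. Items run from 0 to K, with K = 5 as the main case and K = 3 as a shorter scale. True totals are 40 on Day 1 and 15 on Day 14. Each blank item has the patient's average severity on that day.

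**Formula.** With m blank items on a form whose true total is T:

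scored total = T + m × (K - T/22)

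**Main case, K = 5.** True change = (15 - 40)/40 = -62.5%.

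- The error per blank item is 5 - 40/22 = 3.18 points on Day 1 and 5 - 15/22 = 4.32 points on Day 14.
- One Day 1 blank: baseline 43.18, change (15 - 43.18)/43.18 = -65.3%.
- Two Day 1 blanks: baseline 46.36, change (15 - 46.36)/46.36 = -67.6%.
- One Day 14 blank: score 19.32, change (19.32 - 40)/40 = -51.7%.
- Two Day 14 blanks: score 23.64, change (23.64 - 40)/40 = -40.9%.

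| Gap | Shown, K = 5 | Error (percentage points) | Shown, K = 3 | Error (percentage points) |
|---|---|---|---|---|
| None | -62.5% | 0 | -62.5% | 0 |
| 1 item, Day 1 | -65.3% | 2.8 too favourable | -63.6% | 1.1 too favourable |
| 2 items, Day 1 | -67.6% | 5.1 too favourable | -64.6% | 2.1 too favourable |
| 1 item, Day 14 | -51.7% | 10.8 too unfavourable | -56.7% | 5.8 too unfavourable |
| 2 items, Day 14 | -40.9% | 21.6 too unfavourable | -50.9% | 11.6 too unfavourable |

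For K = 3 the per-item errors are 3 - 40/22 = 1.18 points on Day 1 and 3 - 15/22 = 2.32 points on Day 14. The sizes change with the scale; the directions do not.

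**A patient with no real change.** Take K = 5, a true total of 40 throughout, and blank items whose true value is 2. One Day 1 blank gives (40 - 43)/43 = -7.0%; two give (40 - 46)/46 = -13.0%. Over K = 3 to 5, baselines of 20 to 60 and true item values of 0 to 2, the false change runs from -1/61 = -1.6% to -10/30 = -33.3%.

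**Where the error vanishes or shrinks.** If the true answer was already the worst category, K minus the true value is zero and nothing is distorted. If the same average item is blank on both days (K = 5), the change shown is (19.32 - 43.18)/43.18 = -55.3%. That is 7.2 points too unfavourable, against 10.8 for the Day 14 blank alone, so the two errors partly offset.

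**Group level.** The shift in an arm's mean is the share of affected patients times the individual error. If 5% of patients leave one Day 1 item blank, it is 0.05 × 7.0 = 0.35 points in the no-change case and 0.05 × 2.8 = 0.14 points in the 40-to-15 case. At 2% and 20% the no-change figures are 0.14 and 1.40. The documents give no rate of missing items.

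**Effect of prorating.** For the no-change patient, one Day 1 blank gives 38/21 × 22 = 39.8 and a change of +0.5%. Two give 36/20 × 22 = 39.6 and +1.0%. These replace -7.0% and -13.0%.

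**The case against.** The strongest reply is that the favourable error is the smaller one and probably the rarer one. In the main case a Day 14 blank does about four times the damage of a Day 1 blank, in the other direction, so equally frequent gaps would leave the result net unfavourable. The Day 1 form is also the best supervised. It is "documented by patient in the diary during the visit in the clinical site" (Protocol section 9, Visit 2), after the investigator has explained unclear terms (Protocol 9.1). This stands, and it limits the size. It does not justify the rule at baseline, because errors of opposite sign in different patients do not make either patient's score right.

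A second reply is that SNOT-22 is descriptive, untested and outside the hierarchical procedure in SAP 7.4.1, and that individual questionnaires are listed (SAP 7.3.1.2). This also stands and sets the priority.

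A reader might infer that the rule favours acetylcysteine over placebo. The documents do not support that. In the Visit 2 procedures the questionnaire comes before randomization, so Day 1 gaps should be distributed alike across arms apart from chance. A reader might also infer that the SAP wrongly presents this rule as conservative. It does not: the SAP uses worst-case language for the responder endpoint and makes no such claim for SNOT-22.

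**Conclusion.** The point holds as a minor one. The rule as written inflates the Day 1 total whenever a blank item was not truly at its worst, and that carries into percent change as false improvement. After baseline it hides real improvement. With items 0 to 5 and totals of 40 then 15, the error is 2.8 or 5.1 percentage points too favourable for one or two Day 1 blanks, and 10.8 or 21.6 too unfavourable for Day 14 blanks. The directions follow from the SAP's own definitions. The sizes rest on the assumed item range, totals and average-severity blanks.

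It would go too far to say that every patient with a blank item is misreported, or that SNOT-22 results as a whole will look too good. Some blanks cause no error, some partly offset, and the net direction depends on missing-item rates that the documents do not give. What is affected is the description of within-group SNOT-22 scores and changes. The primary endpoint, its error rate and the sample size are not touched.

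**What to change.** In SAP 7.2.5, replace the worst-category rule for Day 1 forms with prorating: with one or two items missing, score = (sum of answered items / number answered) × 22. Keep the rule that more than two missing items makes the score missing.

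Applying the same prorating on Days 7 and 14 is the consistent option and removes the opposite-direction error, but that part is a choice. Prorating assumes that a skipped item resembles the patient's answered ones, and it drops the penalty for gaps after baseline. A team that wants to keep the penalty can retain the worst category on Days 7 and 14 and change Day 1 alone.

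The same sentence should say that the rule covers the PPS: 7.2.5 names only the FAS, while 7.4.2.3 analyses both sets.

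The cost is one sentence and one line of derivation code, with no new data. SAP section 4 allows updates before database lock; after lock, the change belongs in an SAP addendum.

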7.2.6 Interim Analysis

Not applicable.

7.2.7 Protocol Deviations

All protocol deviations will be listed by patient and will be discussed with the sponsor during the Blind Data Review Meeting before unblinding and database lock. Depending on the severity of protocol deviations (minor/major) the patients will be assigned to the respective statistical population.

Possible protocol deviations are discussed in a separate Protocol Deviation Management Plan.

The following categories of protocol deviations were defined in the Protocol Deviation Management Plan:

- Eligibility deviation,
- Withdrawal deviation
- Dosing deviation,
- Prohibited medication and therapies deviation
- Operational deviation

The final decisions regarding the severity of protocol deviations will be documented in a separate Protocol Deviation Report.

The occurred protocol deviations will be assessed by means of frequency tables, see Section [7.3.4.2](#).

7.3 Analysis Variables

7.3.1 Efficacy Variables

7.3.1.1 Major Symptom Score (MSS)

The MSS combines the following symptoms of rhinosinusitis based on expert clinician recommendations

- rhinorrhea/ anterior discharge,
- postnasal drip,
- nasal congestion,
- headache, and
- facial pain/pressure.

Assessment of symptom severity. The patient will rate the severity of each of the five symptoms of the MSS using a four-point rating scale of increasing severity (⊙ = none/not present, ① = mild, ② = moderate, ③ = severe).

The MSS is then the sum of the single ratings.

The MSS will be assessed by the patient at screening (Visit 1) and immediately before randomization (Visit 2; this will constitute the baseline value). The investigator will transcribe both patient's MSS assessments from TSSF into the CRF.

Thereafter, the patient will document the MSS in the patient diary once a day before intake of the morning dose, starting with Day 2 until Day 14 (last day of treatment or earlier in case of drop-out).

The last MSS will be assessed by the patient during Visit 6 and transcribed from TSSF into the CRF.

Statistical evaluation of the MSS is described in section [7.4](#).

7.3.1.2 Sino-Nasal Outcome Test (SNOT-22) Questionnaire

SNOT-22 will be assessed by the patient in the patient diary on Day 1, Day 7 and Day 14.

SNOT-22 will be part of the patient diary printed on no-carbon copy paper (one top page and a second no-carbon copy page). The patient must complete the first SNOT-22 in the patient diary during Visit 2, after the investigator explained unclear terms and answered all patient's questions.

All individual SNOT questionnaire results of the Safety Set will be listed by patient. Further statistical evaluation is described in section [7.4.2](#).

7.3.1.3 Investigator's Assessment of the Overall Response to Treatment

The investigator will assess the overall response to treatment at each visit after baseline: at Visit 3 (Day 4), Visit 4 (Day 7), Visit 5 (Day 10), and at Visit 6 (Day 15 or up to 3 additional days).

The investigator will rate the response to treatment using a five-point rating scale: ① = major deterioration, ② = minor deterioration, ③ = no change, ④ = minor improvement, ⑤ = major improvement.

All individual assessments of overall response of the Safety Set will be listed by patient. Further statistical evaluation is described in section [7.4.2](#)

7.3.2 Demographic and Background Variables

The following demographic and anthropometric information will be recorded:

- Date of informed consent
- Date of birth (in Germany only the year of birth will be recorded)
- Age in years at date of informed consent (derived, whereas age for patients from Germany cannot be derived exactly from the CRF, Discrepancy Clarification Forms will be used to obtain the age of the patients from the investigator)
- Ethnicity (Caucasian, Hispanic, Black, Asian, Unknown or other)
- Gender/ Sex
- Height without shoes (cm)
- Body weight inclusive indoor clothing without shoes (kg)
- Body mass index (BMI) calculated as $[\text{weight}/\text{height}^2]$ (kg/m²)
- Life Style and Habits (alcohol consumption, smoking status and drug abuse history)
- Anamnestic information (last participation in any clinical trial, allergies, ...)
- Anamnesis on Acute Uncomplicated Rhinosinusitis
- Method of contraception (additional anamnesis for female patients only)
- Medical and surgical history (including previous and concomitant diseases)
- Previous medication (drug history)/ therapies (within 6 months prior to screening which stopped before screening)
- Concomitant medication (recorded at screening visit and/or during the trial)
- Medical or therapeutic measures (recorded at screening visit and/or during the trial)

All demographic data and background variables of the Safety Set will be listed by patient, except for the anamnestic information. The anamnestic information is only collected in order to document the eligibility of the patients. Additionally, demographic data of the patients which were only screened but not treated will be listed by patient.

Descriptive statistics for the quantitative data (age, height, weight, BMI) and absolute and relative frequencies of the quantitative data (sex, ethnic group) will be presented for the safety set, the FAS and for the PPS.

The concomitant medication (drug name, indication, administration scheme, dosage form, route of administration, start date and end date of medication) will be listed by patient. The end date will be substituted by the term 'ongoing' if the medication did not stop before termination of the trial. The listings contain the WHO Drug B3 coding up to level 4 for the used drugs, as well as MedDRA (Version 22.1 or higher) for the respective indications.

Frequency tables will be presented for medical and surgical history (including previous and concomitant diseases) and for the previous and concomitant medication.

The medical history will be displayed as incidences (number of findings and number of patients affected) for diseases and surgery which ended before start of the trial (Visit 2) by SOC, PT and treatment group for the safety set.

The concomitant diseases will be displayed as incidences (number of findings and number of patients affected) for diseases and surgery which are present at start of the trial (Visit 2) SOC, PT and treatment group for the safety set.

The previous medication, i.e. medication which stopped before the start of the trial (Visit 2) will be tabulated as numbers of findings and numbers of patients affected by WHO Drug B3 term Level 3, Preferred Name and by treatment group for the safety set.

The concomitant medication which is present at the start of the trial (Visit 2) and which starts during the trial, will be tabulated as numbers of findings and numbers of patients affected by WHO Drug B3 term Level 3, Preferred Name and by treatment group for the safety set.

7.3.3 Safety Variables

All evaluations of the safety variables will be performed in Safety Set.

